The OBJECTIVE of this research protocol is to evaluate the effectiveness of RPP compared to postural drainage plus compression to the muscle belly of the upper limbs, as an adjuvant treatment for children with pneumonia. It is expected that the clinical severity decreases by 1.5 in the Wang score (a modification of the Silverman score), with a standard deviation of 2.6 points and a decrease of two days in the hospital stay with a α 0.05 in a one-tail test, a P of 80% and a 95.5% confidence interval.

METHODOLOGY, the protocol design corresponds to a single-blind trial. The population will consist of children aged from 0 to 8 years old diagnosed with pneumonia with a development time less than 7 days. The participants who comply with the selection criteria will be grouped in blocks of two using a randomization software (www.radomization.com).

The sample calculation corresponds to 40 participants per group. The intervention group will be exposed to techniques such as prolonged slow expiration, controlled expiratory flow exercises, tracheal pumping and tracheal reflex. The control group will be subject to postural drainage plus compressions to the muscle belly of the upper limbs. Both groups will go through 10 sessions: One daily session from Monday to Friday with a duration of 10 to 15 minutes each.

The Wang score (a modification of the Silverman score) will be used to measure the clinical severity and a pulse oximeter ChoiceMMed MD300C5 for SpO_2 and heart rate readings, the medical records will be consulted during the hospital stay.

DATA ANALYSIS PLAN, to prove whether there are or not statistical differences in and between both groups a Mann-Whitney U test will be used. The weightings from the Wang score (a modification of the Silverman score) will be considered before and immediately after the intervention maneuvers, and after 15, 30 and 120 minutes after said maneuvers have been performed.

BACKGROUND

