To evaluate the prolonged effects (15, 30 and 150 minutes after intervention) of RPP on clinical severity (Wang score (a modification of the Silverman score)) in comparison to PD plus muscle belly compressions to the upper limbs for the treatment of a child with in-hospital pneumonia.

To evaluate the effect of RPP compared to PD plus muscle belly compressions to the upper limbs on the number of days of HS of children with pneumonia.

HYPOTHESIS

1. Children with pneumonia who receive RPP Will have a decrease of 1.5 points, with a standard deviation of 2.6 In the Wang score (a modification of the Silverman score), 30 minutes after it being performed.

2. Children with pneumonia will have a decrease in HS of two days, compared to those treated with PD plus muscle belly compressions to the upper limbs.

METHODOLOGY AND RESEARCH DESIGN

DESIGN

Single-blind randomized clinical trial

Population

1. Study universe: Hospitalized children with pneumonia at the infectiology service.

2. Study population: Children from 0 to 8 years old with a diagnostic of pneumonia (under WHO's criteria) with a development time less than 7 days.

3. Sample: With the support of the epidemiology department, a daily list of all new cases of pneumonia will be provided. Patients then will be included once the diagnostic established by the pneumonia infectiology service is obtained.

Sample size calculation

The calculation for a sample size for an error of α 0.05 in a one-tail test and a power of 80% is based on the values described by Postiaux^{*37} in the difference between the groups 30 minutes after the intervention, during 10 sessions. The difference in the Wang score (a modification of the Silverman score) measurements between the two groups was of 1.5 points with a standard deviation of 2.6 points.

 $\label{eq:states} \begin{array}{l} \Delta \texttt{= 1.5} \\ \texttt{S= 2.6} \\ \texttt{n = 2S}^2(\texttt{Z}_{\alpha/2} + \texttt{Z}_\beta)/\Delta^2 \end{array}$

The participants' sample size will be of 40 per group, to obtain statistical differences in the decrease of the Wang score (a modification of the Silverman score) entre between both groups with a α 0.05 in a one-tail test and a power of 80%, considering a decrease of 36% and a standard deviation of 13%.

Randomization

- 1. A sequence of aleatory numbers in blocks of 2 will be generated in each of the study groups using the software randomization.com, done by a person foreign to the research.

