Also accepted as the term expiratory flow acceleration (EFA). It is obtained by the energetic contraction of the expiratory muscles (mainly the abdominal ones). During the maneuver, the intrathoracic pressure of the oral discharge increases simultaneously, which produces a lower mouth discharge that that of coughing, that allows the tearing off of the secretions from the bronchial wall due to the apparition mechanism of the SPP (same pressure point). This situation responds to the function of viscosity, elasticity, mucus thickness, the level of adhesion to the bronchial wall and the flexibility of the bronchial wall.^{*36}

Control Group

The control group (CG) will be subject to PD plus muscle belly compressions of the upper limbs for 10 sessions, one session a day from Monday to Friday, with a duration de 10 to 15 minutes per patient. Both groups will receive the usual treatment for pneumonia prescribed by their treating doctor.

Variables and measuring instruments.

Measurements will be performed before, and 15, 30 and 150 minutes after the maneuvers. Clinical severity will be measured using the Wang score (a modification of the Silverman score) *(Table 3)*, which consists of 4 items:

- 1. Respiratory rate.
- 2. Wheezing.
- 3. Retraction.
- 4. General condition.

Every item has an ordinal measurement level of 0 to 3 points (possible values: 0,1,2,3), excluding general condition (with a value of 0 or 3 only).

With a maximum summation of 12 points and a minimum of 0 points. The higher the score, the higher the clinical severity.

Complementary measurements:

- 1. Heart rate.
- 2. SaO₂.
- 3. Lung occupancy in the x-ray that was taken when the diagnosis was made.

The results from the pediatric Wang score (a modification of the Silverman score) will be compared in and between the groups at the following moments: 1.Before intervention (baseline state), 2.immediately after intervention, 3.15 minutes after intervention and 4.30 minutes after that.

The following tool (anex 2) has been designed to measure the variables. The

resources needed for research development are:

- 1. Medical history.
- 2. Vital signs monitors.
- 3. Stethoscope.
- 4. Pulse oximeter.
- 5. Disposable latex gloves.
- 6. Mechanical aspiration

RESEARCH VARIABLES

Independent variables

- 1. Pediatric respiratory physiotherapy.
- 2. Postural drainage plus muscle belly compressions to the upper limbs.

Dependent variables

- 1. Clinical severity.

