- 3. Another collaborator will do a follow-up on the patients in order to register their hospital stay time posterior to the diagnosis of pneumonia.
- 4. The assigned maneuver will be performed once a day on the patient.

End of study

The study will end once the patient checks out of the hospital.

Quality control

The assessment of the efficiency will be performed by 2 collaborators blinded to the maneuver. One collaborator will assess the Wang score (a modification of the Silverman score), heart rate and SaO_2 and the other collaborator will register the days of HS.

DATA ANALYSIS PLAN

Descriptive statistic: There will be an assessment of the central tendency values, relative dispersion and disposition to evaluate the descriptive variables at the start and at the end of the studyin both groups, as well as the dependent variables after the intervention.

Inferential statistic:

- 1. The comparison in score of the descriptive variables in and between the groups will be performed using a Mann-Whitney U test.
- 2. A 95% confidence Interval is estimated.

The Wang score rates will be assessed in the measurements made before and immediately after the intervention, and 13, 30 and 150 minutes after.

To describe the measurement differences and to reject or not the hypothesis, a Mann-Whitney U test will be used.

LIMITATIONS OF THE STUDY

Due to the maneuver condition, the subject cannot be blinded, and only the researchers will be single-blinded, which confers a type of bias to the study.

TIMELINE

The timeline of activities is presented as a FORMAT ATTACHED to this document.

ETHICAL CONSIDERATIONS

The 2016 guide for the evaluation of ethical considerations of our institution is presented as a FORMAT ATTACHED to this document.

Beneficence/Nonmaleficence

This is a MAXIMUM TO MINIMAL RISK study for participants, and it could cause reflux, vomit or irritability of the patient's emotional state (with all that implies). Potential benefit to the patient by improving their clinical severity and reducing the days of hospital stay. Potential Benefit to society by reducing the days of hospital stay, which in turn will reduce the cost of treatment for children with pneumonia.

Autonomy and respect

It will be clearly expressed to the patient or person responsible for them, every procedure they will become subject to, until their understanding is secured.

A Form of Informed Consent will be required (Anex 3).

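### Two unranked hypotheses, each linked to one-sided 0.05, put the chance of a false claim of effectiveness at about 9 to 10% if either may support it

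*Combined protocol and SAP*

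**What the plan says.** The general objective is one question: whether RPP is effective compared with postural drainage plus upper-limb compressions. Two hypotheses serve it. The first concerns the Wang score 30 minutes after the manoeuvre. The second is that "Children with pneumonia will have a decrease in HS of two days". RESEARCH VARIABLES lists clinical severity and hospital stay as dependent variables without ranking them.

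The level and side of the tests appear in two places. Sample size calculation says "The calculation for a sample size for an error of α 0.05 in a one-tail test and a power of 80" per cent, based on a Wang difference that "between the two groups was of 1.5 points with a standard deviation of 2.6 points", taken "in the difference between the groups 30 minutes after the intervention, during 10 sessions". The SUMMARY gives the expected Wang effect together with "a decrease of two days in the hospital stay with a α 0.05 in a one-tail test".

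The sections differ on the Wang times:
- HYPOTHESIS and Sample size calculation name 30 minutes only.
- The first research question and the first specific objective give 15, 30 and 150 minutes equal weight.
- Variables and measuring instruments says the scores "will be compared in and between the groups at the following moments", then lists baseline, immediate, 15 minutes and a last point that can be read as 30 minutes after the manoeuvre or 30 minutes after the 15-minute reading.
- The DATA ANALYSIS PLAN lists four post-treatment times (immediate, 13, 30 and 150 minutes) and then says "To describe the measurement differences and to reject or not the hypothesis, a Mann-Whitney U test will be used".

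The DATA ANALYSIS PLAN gives no alpha or side for that test, only a 95% confidence interval. No section gives a testing order, a split of alpha or an adjustment.

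**The concern.** When one conclusion can be reached by more than one test, the level of each test is not the error rate of the conclusion. Here a favourable result on either hypothesis could be reported as showing that RPP is effective, and no rule says which result decides.

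This matters because the section on products to be obtained makes presentation at congresses depend on the hypothesis surviving, and the hypotheses are worded as benefits. The JUSTIFICATION also links the result to use of these techniques in the public health system. A reader would take the stated 0.05 as the risk that such a claim is false.

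**Working it through.** **Inputs from the protocol.** One-sided alpha 0.05, power 80%, Wang difference 1.5, SD 2.6, 40 per group (Sample size calculation); one-tail 0.05 for stay (SUMMARY); four post-treatment Wang times (DATA ANALYSIS PLAN).

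**Assumptions.** The protocol gives no correlations between outcomes. I take 0.5 to 0.9 between Wang times and 0 to 0.5 between Wang and stay.

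**1. The plan's own figure.** The usual formula for two means, n = 2S²(Zα + Zβ)²/Δ², gives:
- One-sided 0.05: 2 × 6.76 × (1.645 + 0.842)² / 2.25 = 37.15, so 38 per group. Dividing 37.15 by 0.955 for the efficiency of the Mann-Whitney test gives 38.9, so 39.
- Two-sided 0.05: 48 per group.
- The formula as printed (Zα/2, bracket not squared): 2 × 6.76 × (1.960 + 0.842) / 2.25 = 16.8, about 17.

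The plan states that the "sample size will be of 40 per group". This fits the one-sided calculation and not the two-sided one, which supports reading the intended tests as one-sided 0.05. Power with 40 per group, by normal approximation, is Φ(1.5 / (2.6 × √(2/40)) − 1.645) = Φ(0.935) = 82.5%.

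**2. Two tests: Wang at 30 minutes, and stay.** The chance that at least one is falsely significant is 1 − P(both z-statistics < 1.645).
- Independent: 1 − 0.95² = 9.75%
- Correlation 0.3: 9.3%
- Correlation 0.5: 8.8%

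That is 1.8 to 1.95 times 5%.

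**3. Five tests: any of four Wang times, or stay.** The same formula with a five-variable normal distribution gives:

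| Wang-Wang correlation | Wang-stay 0 | Wang-stay 0.3 | Wang-stay 0.5 |
|---|---|---|---|
| 0.5 | 18.7% | 17.6% | 16.6% |
| 0.7 | 16.4% | 15.5% | 14.7% |
| 0.9 | 13.4% | 12.7% | 12.0% |

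A simulation of Mann-Whitney tests with 40 per group agrees to within about one percentage point: 19.1% for correlations 0.5 and 0, and 13.6% for 0.9 and 0.3. Its two-test results were 9.0 to 9.9%.

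**4. Two-sided 0.05 instead.** Only the favourable tail (0.025) counts as a false claim for RPP.
- Two tests: 1 − 0.975² = 4.9% if independent; 4.5% at correlation 0.5.
- Five tests: 6.5% (Wang-Wang 0.9, Wang-stay 0.5) to 10.1% (0.5 and 0).

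**The case against.** The strongest reply is that the two hypotheses answer two research questions, each with its own endpoint. If each is judged and reported separately, each test carries its own 5%. No section says that one significant result among several establishes effectiveness. This stands as far as it goes: the 9 to 10% applies only if either result may support the general claim. The plan does not rule that out, and the single general objective invites it.

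A reader might infer something stronger: that four unordered Wang times plus stay are each tested at one-sided 0.05, so the error is up to three times 5% or more. The documents do not support that as a statement of fact.
- Hypothesis 1 and the sample size both fix 30 minutes, so the Wang times are not wholly unordered.
- The analysis section can be read as describing all times and deciding only on the stated hypothesis.
- That section gives no alpha or side. One-sided 0.05 is a well-supported inference from the SUMMARY and the sample size. Its 95% interval fits two-sided testing just as well, and then the inflation for two tests disappears.
- The five-test figures rest on correlations that the protocol does not supply.

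The plan allows up to ten sessions and mentions within-group comparisons. Counting these could raise the figure, but no section says that each session is tested, so I put no number on it.

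**Conclusion.** The point holds for the two hypotheses. They are unranked, they serve one effectiveness objective, and the SUMMARY ties one-tail 0.05 to both. If each is tested at that level and either may support effectiveness, the chance of a false claim is about 9 to 10%, nearly twice the stated 5%.

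The range of about 12 to 19% is a scenario. It needs every listed Wang time to count as a decision, which the text allows but does not state, and it depends on assumed correlations. Under two-sided 0.05 testing, the two-test figure is at or below 5%, and the five-test figure is about 6 to 10%. That the answer turns on an unstated side and an unstated decision rule is itself a reason to settle both in the analysis section before the data are seen.

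**What to change.** In the DATA ANALYSIS PLAN:
1. Name the between-group difference in Wang change from baseline to 30 minutes after the manoeuvre as the single primary test. This is the time point and score that set the sample size.
2. State its alpha and sidedness: one-sided 0.05, as in the sample size calculation.
3. Fix in advance which session, or which per-patient summary over sessions, enters the test. Without this the primary test remains undefined.
4. Test hospital stay at the same level only if the primary is significant.
5. Report the other Wang times as estimates with intervals and no decision, and reconcile the list of times across sections.

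The fixed order holds the overall error at 5% without splitting alpha. The sample size stays at 40 per group, with about 82% power for the Wang test by normal approximation, provided that 2.6 is the SD of the quantity tested. Splitting alpha equally (0.025 each) would instead cut that power to 73.2%, or need 48 per group for 80%.

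The change is one of wording, but it has a price. A stay benefit could not be claimed as confirmatory if the Wang test fails, and the 15- and 150-minute results named in the specific objective become supportive only.

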The detriment of respiratory functions is one of the main sequels left by pneumonia, however, its treatment (curative, symptomatic or preventive) is not taken into consideration by the Mexican norm of "prevention and control of acute respiratory infections (ARI's) during first care" NOM-024-SSA2, nor by the 2011 guides for the treatment of nosocomial pneumonia updates from the department of infectiology at the Hospital Infantil de México Federico Gómez. In contrast, countries like Chile, ^{*1,2} Belgium, ^{*3} France, ^{*3,4,5} Spain^{*4,6} and Switzerland^{*7} have turned to RPP during the three levels of public health care as an strategy to combat said detriment.

In Chile, over a million physiotherapists are part of the national program "prevention and handling of acute respiratory infections in children".^{*2}

In Switzerland, 4% of outpatients and 14.4% of hospitalized patients received said treatment during 2006.^{*7}

In Spain, during 2007, 7.3% of nursing babies treated in top class hospitals received RPP.*8

There are reports of its use in countries such as Argentina, ^{*9} Brazil, ^{*10} Israel^{*11} and the United Kingdom. ^{*12,13}

During 1998 to 2008, the mortality rate caused by ARIs decreased in Mexico by 46% and in Chile by 70%.^{*14} There is probability of a co-relation between the inclusion of RPP in Chile's health care system in 1990 and the countries' significant decrease in the rate of mortality by ARIs.

In our country the use of RPP is discrepant due to the use of techniques designed for adults (postural drainage, vibrations and percussions) applied on children, even though in 1994 *the Fédération Française de Kinésithérapie Respiratoire recommended not using it for pediatrics*, *¹⁶ said techniques do not take into consideration the anatomophysiological or mechanical characteristics of newborns, nursing babies and children, which jeopardizes the health of the patient. *¹⁷

The collected published works about the clinical efficiency of RPP are not unanimous in their conclusions.

The strongest evidence of RPP on children with pneumonia comes from a systematic Cochrane review (SCR), *¹⁸ which takes into consideration 3 randomized controlled trials (RCT) ^{*19,20,21} with a total of 255 participants (*Table 1*). The authors consider that the diversity in age range, intervention maneuvers, execution time and methodological inefficiency in the selected articles makes it impossible to reach a conclusion about their efficiency.

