We consider that due to the participants' ages it is not possible to require a Form of Informed Assent.

The anonymity of participants will be maintained, and the confidentiality of data will be maintained using a restricted database to which only the researchers have access to. Justice: The participant population is in a vulnerable situation since they are minors. Nevertheless, the adult population is well enough informed and the results of this study seek to improve the care of this sector of the population.

The norms and standards for bioethics from the declaration of Helsinki have been considered, as well as the legal and juridical regimes for research current on Mexico (General Law of Health in Regard of Research in Human Beings).

BIOSECURITYCONSIDERATIONS

This research project does not have biosecurity implications, since no pathogenic agents or potential pathogens are handled.

The form from the biosecurity committee of our nation is presented as a FORMAT ATTACHED to this document.

PRODUCTS TO BE OBTAINED FROM THE STUDY

Assuming that the biostatistical results gathered do not reject the hypothesis, it is intended to divulge the results by elaborating a scientific poster and presenting it in various congresses and update conferences.

The following events are contemplated to divulge the results:

- 1. IIV Conferencia de actualización en pediatría. ALEPE. 2017.
- 2. 76° Congreso de las Américas de Neumología y Cirugía de Tórax. Sociedad Mexicana de Neumología y Cirugía de Tórax. 2017.
- 3. XVI International Congress on Pediatric Pulmonology. CIPP. 2017.
- 4. 49° Congreso Nacional SEPAR. 2017.
- 5. LXIV Congreso de la Asociación de Médicos del Hospital Infantil. 2017.
- 6. VII Congreso de SEFIP. 2017.

BIBLIOGRAPHIC REFERENCES

[1] Girardi G, et al. El Programa IRA en Chile: hitos e historia. [IRA program in Chile: milestones and history] Chil Ped (Chil). 2001; 72: 292-300.

[2] Ministerio de Salud. Programa Nacional de Prevención y Manejo de Infecciones Respiratorias Agudas del Niño. [Ministry of Health. National Program for the Prevention and Handling of Acute Respiratory Infections in a Child] Chile: Gob Chil; 2007.

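### The only dissemination the protocol names depends on the results not rejecting the hypothesis, and nothing provides for reporting a null or unfavourable result

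*Combined protocol and SAP*

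**What the plan says.** PRODUCTS TO BE OBTAINED FROM THE STUDY opens with a condition: "Assuming that the biostatistical results gathered do not reject the hypothesis, it is intended to divulge the results". The sentence continues with the route, "by elaborating a scientific poster and presenting it in various congresses and update conferences", and six events follow. No journal article, registry posting or institutional report is mentioned there or elsewhere.

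The HYPOTHESIS section lists two statements, both in favour of RPP. The first concerns the Wang score at 30 minutes: "Children with pneumonia who receive RPP Will have a decrease of 1.5 points, with a standard deviation of 2.6". The second concerns hospital stay (HS): "Children with pneumonia will have a decrease in HS of two days, compared to those treated with PD" plus muscle compressions. No null hypothesis is written down.

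The DATA ANALYSIS PLAN uses the same language: "To describe the measurement differences and to reject or not the hypothesis, a Mann-Whitney U test will be used". It also says that a 95% confidence interval is estimated, without naming the quantity it belongs to.

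ETHICAL CONSIDERATIONS refers in general terms to the Declaration of Helsinki and Mexican research law. It contains no commitment on reporting results.

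**The concern.** A reporting rule that looks at the result before deciding whether to report is selective reporting by design, even if none is intended. The estimate shown to readers is then drawn from a truncated distribution, and its mean differs from the true effect.

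This matters for the protocol's own case. BACKGROUND says "The collected published works about the clinical efficiency of RPP are not unanimous in their conclusions", and Table 1 summarises the three trials in the cited systematic review as finding no difference or no statistical significance. The protocol therefore relies on others having published null results, while making no provision to publish one itself. JUSTIFICATION argues that without this study the techniques will go on being prescribed empirically; a null result would bear on that as much as a favourable one.

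The wording raises a second, smaller problem. A Mann-Whitney test addresses a null of no difference between groups. Failing to reject a research hypothesis of 1.5 points or two days is not evidence for it, so the condition does not say clearly which results would satisfy it.

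**Working it through.** **1. What the text establishes.**
- Condition: dissemination follows if the results do not reject the hypothesis (PRODUCTS TO BE OBTAINED FROM THE STUDY).
- Hypotheses stated: lower Wang score and shorter stay with RPP (HYPOTHESIS).
- Alternative route for other results: none found in any section.

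Together these mean that the named dissemination depends on the result and that a null or unfavourable result has no stated route. This step needs no arithmetic.

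**2. Inputs for the illustration.** From Sample size calculation: "error of α 0.05 in a one-tail test and a power of 80" percent; a difference in Wang score "measurements between the two groups was of 1.5 points with a standard deviation of 2.6 points"; 40 per group.

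The plan's own figure comes first. With the sum of the z values squared, n = 2 × 2.6² × (1.645 + 0.842)² / 1.5² = 37.15, so 38 per group. The stated 40 is within two of this, so a one-sided 0.05 test with these inputs is a fair basis. The point does not rest on the sample size.

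**3. Standard error and cut-offs** (normal approximation, Wang score only).
- SE = 2.6 × √(2/40) = 0.581.
- Reading A, a significant result for RPP: estimate above 1.645 × 0.581 = 0.956.
- Reading B, the literal one, an estimate not significantly below the hypothesised 1.5: estimate above 1.5 − 0.956 = 0.544.
- Reading C, the hypothesis is an unstated null of no difference: estimate at or below 0.956.

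**4. Formulas.** For true difference d and cut-off c, let a = (c − d)/SE, with φ and Φ the standard normal density and distribution function.
- Selected above c: the mean disseminated estimate is d + SE × φ(a)/(1 − Φ(a)), and the proportion not disseminated is Φ(a).
- Selected at or below c: the mean is d − SE × φ(a)/Φ(a), and the proportion not disseminated is 1 − Φ(a).

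**5. Worked at d = 0.75** (an assumed value, half the planned effect).
- A: a = (0.956 − 0.75)/0.581 = 0.355; Φ = 0.639; φ = 0.3746. Mean = 0.75 + 0.581 × 0.3746/0.361 = 1.35. Not disseminated: 64%.
- B: a = (0.544 − 0.75)/0.581 = −0.355; Φ = 0.361. Mean = 0.75 + 0.581 × 0.3746/0.639 = 1.09. Not disseminated: 36%.
- C: a = 0.355. Mean = 0.75 − 0.581 × 0.3746/0.639 = 0.41. Not disseminated: 36%.

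Relative to 0.75, reading A overstates by about 80% (1.35/0.75), B overstates by about 45% (1.09/0.75), and C understates by about 45% (0.41/0.75).

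**6. Range over the true difference** (mean disseminated estimate; percent not disseminated).

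| True difference | Reading A | Reading B |
|---|---|---|
| 0 | 1.20; 95% | 0.86; 83% |
| 0.75 | 1.35; 64% | 1.09; 36% |
| 1.5 | 1.68; 17% | 1.56; 5% |

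Under A and B the distortion is largest when the true effect is small and modest when it equals the planned 1.5.

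**The case against.** A reader might infer that null results will be withheld and that the public record of this trial can only be favourable. The documents do not support that. The sentence contains no exclusive wording, it concerns a poster and congresses, and it is silent on other outlets. What can be said is that no provision is made for a null or unfavourable result.

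A reader might also infer that any reported effect must be biased upward. That holds under readings A and B but reverses under C. The protocol states no null, so C is the less natural reading, but the wording does not exclude it. Nor can a single set of figures be quoted as the size of the bias.

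The document reads as a translation, and the condition may be loose wording for results that support the hypothesis. That weakens any charge that the investigators plan to treat non-rejection as proof of benefit. It does not remove the condition.

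Three further points are fair. An interval is already planned. The unstated null is a separate and secondary matter. And the clause affects neither randomisation, measurement, analysis nor participant safety. All three stand, and they limit the weight of the point without answering it.

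**Conclusion.** The point holds in this form: the only named dissemination is conditional on the result, the stated hypotheses all favour RPP, and there is no provision for reporting anything else. Under every reading examined, what is disseminated is selected on the outcome.

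The size is illustrative. At a true difference of 0.75 points the mean disseminated estimate ranges from about 0.41 to about 1.35, according to the reading. This assumes a normal approximation in place of the Mann-Whitney test, the plan's SD and sample size, a one-sided 0.05 level, and that the Wang hypothesis concerns the between-group difference, as the sample size section treats it. Hospital stay is not covered. The condition speaks of one hypothesis while the protocol states two, so how a split result would be handled is unknown.

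The change should be made: the defect is explicit in the text and the remedy costs almost nothing.

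**What to change.** In PRODUCTS TO BE OBTAINED FROM THE STUDY, delete the opening condition and state that the results for both hypotheses, Wang score and hospital stay, will be reported whatever their direction or statistical significance.

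As a secondary clarification in the DATA ANALYSIS PLAN, state that the Mann-Whitney test addresses a null of no difference between groups, that support for RPP means rejecting that null in its favour, and that the 95% interval already planned applies to the between-group difference.

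The cost is a few sentences of protocol wording. Patients, sample size and procedures are unchanged.
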